8.5.5. Height and Weight

Height will be measured at Screening only. Weight is to be measured at the time points designated in Table 1.

The patient's Screening weight is to be used to calculate the study drug dose. If the patient has experienced a notable change in weight ($\pm 10\%$), the patient's study drug dose

will be recalculated. Any change in study drug dose is to be documented in the source documents and in the eCRF.

8.5.6. Immunogenicity Measurements

Blood samples for determination of Jo-1 Ab levels in serum will be collected at the time points designated in Table 1. Those with a level considered equivocal or positive (ie, >7 U/mL) for the assay will not receive study drug. Any patients who develops positive Jo-1 antibodies will also be monitored clinically for signs/symptoms of anti-synthetase syndrome.

In addition, blood samples for determination of ADAs against ATYR1923 in serum will be collected at the time points designated in Table 1. ADA blood samples collected during Screening from patients who subsequently are determined to be screen failures will be used towards additional modification and validation of the ADA assay.

Blood samples will be processed as described in the Laboratory Manual and evaluated for the presence of ADAs. The exact times of blood sampling will be recorded in the eCRF.

8.5.7. Adverse Events

AEs will be recorded from the time of written informed consent through the last visit for a patient. Any clinically significant observations in results of clinical laboratory, 12-lead ECGs, vital signs, pulse oximetry, or physical examinations are to be recorded as part of the patient's medical history if occurring prior to start of dosing and as an AE if occurring after the start of study drug administration at Day 1, where the finding represents a change from Baseline.

A TEAE is defined as any event not present prior to (the first) administration of the study drug or any event already present that worsens in either intensity or frequency following exposure to the study drug.

An AE which occurs prior to (the first) administration of the study drug will be considered a pre-treatment AE.

AEs that occur during or within 24 hours after study drug injection should be captured as individual signs and symptoms (eg, dyspnea, rash, flushing) rather than a diagnosis of allergic reaction or IRR.

At study visits, patients will be asked non-leading questions to determine the occurrence of AEs. Patients will be asked in general terms about any AEs at regular intervals during the study. In addition, all AEs reported spontaneously during the course of the study will be recorded.

The intensity of each AE will be rated by the Investigator using the National Cancer Institute Common Terminology Criteria for Adverse Events (NCI CTCAE), version 5.0 (available

at: https://ctep.cancer.gov/protocolDevelopment/electronic_applications/docs/CTCAE_v 5_Quick_Reference_8.5x11.pdf).

AEs not listed on the NCI CTCAE are to be rated by the Investigator as "mild (Grade 1)", "moderate (Grade 2)", "severe" (Grade 3), "life-threatening" (Grade 4), or "fatal" (Grade 5).

The relationship between the AEs and the study drug will be indicated as "not related", "unlikely related", "possibly related", or "related". AEs assessed as "possibly related" or "related" will be considered to be related to the study drug whereas AEs assessed as "not related" or "unlikely related" will be considered not to be related to the study drug.

Details on the rating of the severity of the AEs and relationship to the study treatment are given in Section 9.2.

8.5.8. Concomitant Medications

All medications and supplements the patient receives during the course of the study are to be documented in the source documents and in the eCRF.

8.5.9. Safety Laboratory Tests

Blood and urine samples for clinical laboratory assessments will be collected according to the Laboratory Manual and study center standard operating procedures (SOPs).

The following parameters will be measured:

- Clinical chemistry (serum quantitatively):
 - Total bilirubin, alkaline phosphatase, gamma glutamyl transferase (gamma-GT), aspartate aminotransferase (AST), alanine aminotransferase (ALT), lactate dehydrogenase (LDH), creatine phosphokinase, albumin, creatinine, blood urea nitrogen, total protein, glucose, inorganic phosphate, sodium, potassium, calcium and chloride, complete lipid panel.
- Hematology (blood quantitatively):
 - Leukocytes, erythrocytes, hemoglobin, hematocrit, thrombocytes, partial automated differentiation (lymphocytes, monocytes, eosinophils, basophils, neutrophils), mean corpuscular volume, mean corpuscular hemoglobin, mean corpuscular hemoglobin concentration
- Coagulation (blood quantitatively):
 - Prothrombin time (reported in seconds and as international normalized ratio) and partial thromboplastin time
- Urinalysis (semi-quantitative by dipstick):
 - Hemoglobin, urobilinogen, ketones, glucose, protein

- Microscopy is to be performed if indicated by an abnormal and clinically significant result
- Serum Complement, Tryptase/Plasma Complement and immunoglobulin E (IgE):
 - Blood samples for serum complement, tryptase/plasma complement and IgE are to be collected at Day 1. Such test are to be repeated if a patient experiences an IRR (see Section 9.9).

In case of unexplained or unexpected clinical laboratory test values, the tests will be repeated as soon as possible and followed up until the results have returned to the normal range, baseline level and/or an adequate explanation for the abnormality is found. The clinical laboratory will clearly mark all laboratory test values that are outside the normal range and the Investigator will indicate which of these deviations are clinically significant. These clinically significant deviating laboratory results will then be recorded as AEs and the relationship to the treatment will be indicated (see also Section 9.2).

The procedures for the collection, handling, and shipping of laboratory samples are specified in the Laboratory Manual provided to the study site.

8.5.10. Pregnancy Testing and Follicle Stimulating Hormone

FSH will be measured in all female patients during Screening. Female patients of childbearing potential must have a serum pregnancy test performed during Screening and a urine pregnancy test performed at Day 1 prior to first study drug infusion. Any patient with a positive pregnancy test result is not eligible for study participation.

Additional pregnancy testing is to be performed during the study at the time points indicated in Table 1. Pregnancy test results are to be obtained and confirmed to be negative prior to randomization and study drug infusions.

All serum samples will be analyzed by the central laboratory, and urine samples will be analyzed locally. Any patient determined to be pregnant during study participation must have study drug permanently discontinued immediately (see Section 6.4.1 and Section 9.8).

8.5.10.1. Total of Blood Volume

The total volume of blood to be collected over the duration of the study is approximately 450 mL (ranging from 30 mL to 75 mL per visit).

8.5.11. Appropriateness of Measurements

The assessments, which will be made in this study are standard, and generally recognized as reliable, accurate and relevant. Assessments will be performed according to the study site.

9. ADVERSE EVENTS

9.1. **Definitions**

9.1.1. Adverse Event

An AE is defined in the ICH Guideline for GCP as "any untoward medical occurrence in a patient or clinical investigation subject administered a pharmaceutical product and that does not necessarily have a causal relationship with this treatment" (ICH E6:1.2).

Worsening of a pre-existing medical condition, (ie, diabetes, migraine headaches, gout) is to be considered an AE if there is either an increase in severity, frequency, or duration of the condition or an association with significantly worse outcomes.

Interventions for pretreatment conditions (ie, elective cosmetic surgery) or medical procedures that were planned before study enrollment are not considered AEs.

In the case of death, only record "Fatal" for the event causing death. AEs that are ongoing at the end of the study or time of death are to be noted as "continuing."

The Investigator is responsible for reviewing laboratory test results and determining whether an abnormal value in an individual patient represents a significant change from baseline. In general, abnormal laboratory findings without clinical significance (based on the Investigator's judgment) should not be recorded as AEs; however, laboratory value changes requiring therapy or adjustment in prior therapy are considered AEs.

9.1.2. Suspected Adverse Reaction

A suspected adverse reaction is any AE for which there is a reasonable possibility that the drug caused the AE. For the purposes of Investigational New Drug Application (IND) safety reporting, "reasonable possibility" and/or at least possibly related means there is evidence to suggest a causal relationship between the drug and the AE. A 'suspected adverse reaction' implies a lesser degree of certainty about causality than 'adverse reaction', which means any AE caused by a drug.

9.1.3. Serious Adverse Event

An AE or suspected adverse reaction is considered "serious" if, in the view of either the Investigator or Sponsor, it results in any of the following outcomes:

- is fatal
- is life-threatening (ie, places the patient at immediate risk of death)
- requires in-patient hospitalization (overnight stay) or prolongation of existing hospitalization
- results in persistent or significant disability/incapacity
- is a congenital anomaly/birth defect

• is an important medical event; an important medical event is an event that may not result in death, be life-threatening, or require hospitalization but may be considered an SAE when, based upon appropriate medical judgment, it may jeopardize the patient and may require medical or surgical intervention to prevent one of the outcomes listed in the definitions for SAEs. Examples of such medical events include allergic bronchospasm requiring intensive treatment in an emergency room or at home, blood dyscrasias or convulsions that do not result in inpatient hospitalization, or the development of drug dependency or drug abuse.

A hospitalization meeting the regulatory definition for "serious" is any inpatient hospital admission that includes a minimum of an overnight (\geq 24 hours) stay in a health care facility. Any AE that does not meet one of the definitions of serious (ie, emergency room visit, out-patient surgery, or requires urgent investigation) may be considered by the Investigator to meet the "important medical event" criterion for classification as an SAE.

9.1.4. Unexpected Adverse Event

An AE or suspected adverse reaction is considered "unexpected" if it is not listed in the Investigator's Brochure or is not listed at the specificity or intensity that has been previously observed; or, if an Investigator's Brochure is not required or available, is not consistent with the risk information described in the General Investigational Plan or elsewhere in the current application, as amended.

9.1.5. Serious and Unexpected Suspected Adverse Reaction

A SUSAR is any event that meets all 3 of the following definitions:

- 1) suspected adverse reaction (Section 9.1.2);
- 2) serious (Section 9.1.3); and
- 3) unexpected (Section 9.1.4).

9.2. Adverse Event Assessment

All AEs will be collected and recorded in this study from the time of written informed consent through the last visit for a patient. This includes AEs the patient reports spontaneously, those observed by the Investigator, and those elicited by the Investigator in response to open-ended questions during scheduled study visits.

AEs that occur during or within 24 hours after study drug infusion are to be captured as individual signs and symptoms rather than a diagnosis of allergic reaction or IRR.

Each AE is to be assessed by the Investigator with regard to the following categories.

Serious/Non-Serious

AEs that meet the criteria specified in Section 9.1.3 are to be considered serious.

Relationship to Study Drug

This determination is based on the Investigator's clinical judgment regarding the likelihood that the study drug caused the AE and may include consideration of some or all of the following factors:

- Alternative possible causes of the AE, including the patient's underlying disease or co-morbid conditions, other drugs, other host and environmental factors;
- The chronological relationship between the exposure to study drug and the AE;
- Whether the clinical or laboratory manifestations of the AE are consistent with known actions or toxicity of the study drug;
- Whether the AE resolved or improved with decreasing the dose or stopping the study drug (i.e., dechallenge);

Whether the AE recurred or worsened with re-exposure to the drug (i.e., rechallenge).

The relationship between the study drug and the AE will be described using one of the following categories Table 3.

Table 3: Criteria for Determination of Adverse Event Relationship to Study Drug

Relationship	Definition
Related	The study drug is more likely the cause of the AE than other factors
Possibly Related	There is a reasonable possibility that the study drug is the cause of the AE, including that the study drug and another factor(s) are equally likely as causes of the AE
Unlikely Related	Another factor is considered more likely the cause of the AE than the study drug
Not related	Another factor is considered to be the cause of the AE

Intensity

The intensity of each AE is to be assessed by the Investigator using the NCI CTCAE, version 5.0 (available

at: https://ctep.cancer.gov/protocolDevelopment/electronic_applications/docs/CTCAE_v 5_Quick_Reference_8.5x11.pdf).

AEs not listed on the NCI CTCAE are to be rated by the Investigator according to the categories in Table 4.

Table 4: Criteria for Determination of Adverse Event Intensity

Intensity	Definition
Mild (Grade 1):	Asymptomatic or mild symptoms: clinical or diagnostic observations only; intervention not indicated.
Moderate (Grade 2)	Minimal, local, or non-invasive intervention indicated; limiting age- appropriate instrumental activities of daily living.
Severe (Grade 3):	Severe or medically significant but not immediately life threatening: hospitalization or prolongation of hospitalization indicated; disabling; limiting self-care activities of daily living; incapacitating with inability to work or perform normal daily activity.
Life-threatening (Grade 4):	Consequences: urgent intervention indicated.
Fatal (Grade 5)	AE resulted in death

Outcome

The outcome of each AE will be described using the categories in Table 5.

Table 5: Criteria for Determination of Adverse Event Outcome

Outcome	Definition
Resolved without sequelae:	The event resolved and patient returned to baseline
Resolved with sequelae:	The event resolved but the patient is left with residual problems (e.g., functional deficits, pain)
Resolving	At the last observation, the event was improving
Not Resolved	At the last observation, the event was unchanged
Death (Fatal)	To be used for the one AE which, in the judgment of the Investigator, was the primary cause of death
Unknown	There were no observations after the onset (initial observation or report) of the event

Study Drug Action

For each AE, the Investigator will indicate the action taken regarding the administration of study drug per the categories in Table 6.

Table 6: Study Drug Action Taken as a Result of Adverse Events

Action	Definition
Discontinued (withdrawn)	Study drug was stopped permanently due to the AE
Dosing Interrupted	Study drug regimen was modified by being temporarily halted, ie, one or more doses were not administered, but drug was not stopped permanently
Dose Decreased	Study drug regimen was modified by subtraction, ie, by decreasing the frequency, strength or amount
Dose Increased	Study drug regimen was modified by addition, ie, by increasing the frequency, strength or amount
None	No change in the administration of study drug

9.3. Recording Adverse Events

All AEs occurring from the time of written informed consent through the last follow-up visit, or after the end of the study, if thought to be related to study drug, are to be recorded in the source documents and in the eCRF. All AE reports are to contain the following details regarding the AE: a brief description, onset date and time, resolution date and time, intensity, treatment required, relationship to study drug, action taken with study drug, outcome, and whether the event is classified as serious.

AEs that occur during or within 24 hours after study drug injection should be captured as individual signs and symptoms (eg, dyspnea, rash, flushing) rather than a diagnosis of allergic reaction or IRR.

9.4. Reporting Serious Adverse Events

SAEs will be collected and recorded throughout the study period, beginning with the signing of the ICF through the last follow-up visit, or after the end of the study if thought to be related to study drug.

The Investigator must report all SAEs within 24 hours of discovery to the Contract Research Organization (CRO) Safety Team.

SAE reporting, including supporting materials, will be performed by the study center personnel using a system approved by the Sponsor. Detailed training will be provided by the CRO. Contact information for guidance and assistance with SAE reporting is provided in the Study Reference Manual. A completed SAE report is to be entered into the system approved by the Sponsor within 24 hours of discovering the event. Upon entry

into the system, the responsible parties (including Medical Monitor and Safety Reporting Specialist) will be immediately notified.

The Study Reference Manual will include an emergency back-up paper based reporting system, to be used if needed.

The CRO Safety Team will immediately (within one business day of receipt) forward the SAE report to the Sponsor. The initial report should include at least the following information:

- Patient's ID number;
- Description and date of the event;
- Criterion for serious; and
- Preliminary assignment of causality to study drug.

The Medical Monitor may contact the Investigator via telephone for urgent follow-up information regarding the SAE, as appropriate.

The Investigator, or designated party, should notify the appropriate IRB/IEC of SAEs occurring at the study center and other AE reports received from aTyr, in accordance with local procedures and statutes.

SAEs that are considered as possibly or definitely related to the investigational product, and as unexpected (ie, SUSARs), will be reported to the National Regulatory Authority(ies) and IRB/IEC by the Sponsor or Sponsor's designee as required by applicable local regulations. Per regulation, any fatal or life-threatening SUSAR will be reported to the National Regulatory Authority(ies)/IRB/IEC within 7 calendar days, and additional information within an additional 8 calendar days. The Sponsor or Sponsor's designee is required to submit any other SUSAR to the National Regulatory Authority(ies)/IRB/IEC within 15 calendar days of notification. The Sponsor or its designee is also responsible for notifying the investigational sites of all expedited SAEs, in accordance with local requirements. The Investigator must keep copies of all expedited SAE information including correspondence with the Sponsor on file.

9.5. Follow-Up of Adverse Events

The Investigator must continue to follow all study drug-related TEAEs either until resolution or the Investigator assesses them as chronic or stable. This follow-up may extend after the end of the study and may be conducted by telephone contact or unscheduled visit.

9.6. Reporting Safety Information

The Investigator must promptly report to his or her IRB/IEC all unanticipated problems involving risks to patients, in accordance with local requirements. This may include death

65

from any cause and all SAEs reasonably or possibly associated with the use of study drug according to the IRB/IEC's procedures.

9.7. Protocol Deviations Due to an Emergency or Adverse Event

Departures from the protocol will be determined as allowable on a case-by-case basis and only in the event of an emergency (e.g., COVID-19 public health emergency). The Investigator or other physician in attendance in such an emergency must contact the Medical Monitor as soon as possible to discuss the circumstances of the emergency.

The Medical Monitor, in conjunction with the Investigator, will decide whether the patient should continue to participate in the study. All protocol deviations and reasons for such deviations must be noted in the eCRF. Deviations specifically due to COVID-19 are to be documented as such.

9.8. Pregnancy

Pregnancies occurring while the patient is receiving study drug or within 30 days after the patient's last dose of ATYR1923 will not be considered serious, but are to be reported using the same procedures as for SAEs described in Section 9.4.

In the event of a pregnancy, the patient should be referred to an obstetrician/gynecologist experienced in reproductive toxicity for further evaluation and counseling.

The Investigator will follow the patient until completion of the pregnancy, and must notify the Medical Monitor of the outcome within 5 days. The Investigator will provide this information as a follow-up to the initial report.

If the outcome of the pregnancy meets the criteria for immediate classification as an SAE (ie, spontaneous abortion [any congenital anomaly detected in an aborted fetus is to be documented], stillbirth, neonatal death, or congenital anomaly), then the Investigator should report it as such. Furthermore, all neonatal deaths that occur within 30 days of birth are to be reported, without regard to causality, as SAEs. In addition, any infant death after 30 days that the Investigator suspects is related to the in utero exposure to the study drug should also be reported.

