ATYR1923 may provide a naturally occurring human immunomodulatory function to therapeutically control or balance the human immune system. The mechanism of action of ATYR1923 in T-cells overlaps with the cellular pathology observed in lung sarcoidosis. In nonclinical studies, ATYR1923 has been shown to inhibit cytokines involved in regulation of inflammatory and immune responses and attenuate T-cell activation (Mertsching et al, 2018). As NRP2 was recently discovered to bind ATYR1923, and innate immune cells such as dendritic cells and macrophages are known to express NRP2 (Roy et al, 2017; Schellenburg et al, 2017), further research into the interaction between ATYR1923 and NRP2 on these cells could potentially elucidate additional mechanism through which ATYR1923 modulates the immune system. Finally, ATYR1923 has been shown to significantly reduce lung fibrosis and inflammation in bleomycin-induced animal models of ILD (Nangle et al, 2017; Ogilvie et al, 2018).

To date, 25 healthy adult subjects have been exposed to ATYR1923 at doses ranging from 0.03 to 5.0 mg/kg in a first-in-human clinical study, ATYR1923-C-001. Data from this study demonstrated single doses of ATYR1923 over the dosing range of 0.03 to 5 mg/kg to be well-tolerated in healthy volunteers No severe treatment-emergent adverse events (TEAEs), serious adverse events (SAEs), or TEAEs leading to study drug modification (dose reduction or discontinuation) were reported. No apparent dose relationship was seen across the range of doses studies with regard to the incidence of TEAEs. Adverse reactions reported to date include headache, dizziness, and back pain.

No ATYR1923-treated subject experienced a definitive infusion-related reaction (IRR). However, the occurrence of an IRR could not be ruled out for 1 subject, who experienced mild, transient symptoms of dizziness, abdominal pain, and "feeling cold" followed by back pain after ATYR1923 infusion. No subject was positive for anti-drug antibodies (ADA) or Jo-1 Ab after ATYR1923 exposure.

ATYR1923 pharmacokinetics (PK) were dose-proportional over the range of 0.03 mg/kg to 5.0 mg/kg, and the mean half-life ($t_{1/2}$) was consistent at doses of 0.1 mg/kg and above, with mean values ranging from 167 to 242 hours (7 to 10 days), supporting the potential for convenient dosing on a monthly basis.

This study represents the first clinical investigation of ATYR1923 in patients with pulmonary sarcoidosis.

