7.1.6.4. Contraception

For this study, male patients will be considered to be of non-childbearing potential if they have azoospermia (whether due to having had a vasectomy or due to an underlying medical condition).

Female patients will be considered of non-childbearing potential if they are either surgically sterilized (eg, hysterectomy and/or bilateral oophorectomy, bilateral salpingectomy or bilateral tubal ligation/occlusion) or at least 1 year postmenopausal (confirmed by amenorrhea duration of at least 12 months and serum FSH ≥30 mIU/mL).

Female patients of childbearing potential must be non-pregnant and non-lactating, and have a negative pregnancy test at Screening (serum) and at Day 1 (urine) prior to first study drug infusion. A urine pregnancy tests must be repeated at Weeks 8 and 16 and a serum pregnancy test must be repeated at Week 24.

Female and male patients of childbearing potential must agree to avoid becoming pregnant or impregnating a partner, respectively, while receiving study drug and for 90 days after the last dose of study drug by complying with one of the following:

- Practice abstinence¹ from heterosexual activity. (If a patient who was initially abstinent decides to be sexually active during study participation, the patient must agree to use highly-effective contraception, as outlined below.)
 OR
- Use (or have their partner use) highly-effective contraception during heterosexual activity. Examples of highly-effective methods of contraception include:

Single method (one of the following is acceptable):

- Intrauterine device.
- Vasectomy of a female patient's exclusive male partner.

Abstinence (relative to heterosexual activity) can be used as the sole method of contraception if it is consistently employed as the patient's preferred and usual lifestyle and if considered acceptable by local regulatory agencies and IRB/IEC. Periodic abstinence (eg, calendar, ovulation, symptothermal, post-ovulation methods) and withdrawal are not acceptable methods of contraception.

Contraceptive rod implanted into the skin.

Combination method (requires use of two of the following):

- Diaphragm with spermicide (cannot be used in conjunction with cervical cap/spermicide).
- Cervical cap with spermicide (nulliparous women only).
- Contraceptive sponge (nulliparous women only).
- Male condom or female condom (cannot be used together).

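### Section 9.8 requires an initial pregnancy report only up to 30 days after the last dose, 60 days before the contraception period in 7.1.6.4 ends

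*Protocol*

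**What the plan says.** Three parts of the protocol bear on this.

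- **Reporting (9.8).** The initial report covers "Pregnancies occurring while the patient is receiving study drug or within 30 days after" the last dose, by the SAE procedures of 9.4. The limit concerns when the pregnancy occurs, not how long it is followed: "The Investigator will follow the patient until completion of the pregnancy". That duty is then tied to a report already made: "The Investigator will provide this information as a follow-up to the initial report".
- **Later events.** The outcome sentences of 9.8 carry no stated limit in days after dosing. One begins "If the outcome of the pregnancy meets the criteria for immediate classification as an SAE" and lists spontaneous abortion, stillbirth, neonatal death and congenital anomaly. Another adds "any infant death after 30 days that the Investigator suspects is related to the in utero exposure"; its 30 days run from birth, not from the last dose. Section 9.4 collects SAEs to the last follow-up visit, "or after the end of the study if thought to be related to study drug".
- **Contraception.** Section 7.1.6.4 requires patients to avoid pregnancy "while receiving study drug and for 90 days after the last dose of study drug". Inclusion criteria 6 and 7 (synopsis and 5.1.1) count the 90 days from the last follow-up visit instead.

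The last scheduled pregnancy test is at Week 24, nominally 28 days after the sixth dose. Under 4.1.3, follow-up past that visit applies only to confirmed positive Jo-1 titers or ongoing drug-related TEAEs.

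**The concern.** The sponsor asks patients to avoid pregnancy until at least day 90 after the last dose but asks sites to report a pregnancy only if it occurs by day 30. A contraceptive failure between those dates is an event the protocol tries to prevent and does not clearly require anyone to report. A pregnancy is not itself serious under 9.8, so the post-study SAE rule in 9.4 does not bring it in unless something goes wrong and is attributed to the drug.

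If only adverse outcomes of later pregnancies are reportable, the pregnancy record keeps the bad outcomes and loses the normal ones. That record is worth having complete: this is the first study of the drug in patients with pulmonary sarcoidosis, and women of childbearing potential may enrol. Most patients have no scheduled contact after Week 24, so the site would learn of a later pregnancy only if the patient called.

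**Working it through.** **1. Dates.** Inputs: last dose at Week 20 = Day 141 and End-of-Study visit at Week 24 = Day 169 (Table 1); 30 days (9.8); 90 days after last dose (7.1.6.4); 90 days after last follow-up visit (5.1.1). All six doses given, visits on nominal days.

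| Rule | End date | Beyond the 9.8 limit |
|---|---|---|
| 9.8 initial report | 141 + 30 = Day 171 | – |
| 7.1.6.4 contraception | 141 + 90 = Day 231 | 60 days |
| 5.1.1 contraception | 169 + 90 = Day 259 | 88 days |

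The 60 days hold for any number of doses, since both rules count from the last dose. The 88 days are nominal: a missed last dose or extended follow-up under 4.1.3 would lengthen them.

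**2. Half-life.** Section 2.2 gives "mean values ranging from 167 to 242 hours (7 to 10 days"). Check: 167/24 = 6.96 days and 242/24 = 10.08 days, which reproduces the stated days.

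**3. Residual drug at day 30.** Inputs, from 7.1.4.2 for a single 5 mg/kg dose: observed Cmax 109,250 ng/mL and AUC(0–168h) 3,417,001 ng·h/mL. Assumption: the half-life at 5 mg/kg lies within the range in 2.2.

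First test whether decline is a single exponential from peak. In that case AUC(0–168h) = (Cmax/k)(1 − e^(−168k)), with k = ln 2 / half-life.

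- 167 h: k = 0.004151; 26.32 million × 0.5021 = 13.2 million ng·h/mL.
- 242 h: k = 0.002864; 38.14 million × 0.3820 = 14.6 million ng·h/mL.

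These are 3.9 and 4.3 times the observed AUC, so levels fall much faster than that at first. The terminal phase cannot contribute more than the whole observed AUC, which bounds its starting level:

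- 167 h: 3.417/13.215 = 26% of peak.
- 242 h: 3.417/14.569 = 23% of peak.

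The fraction of the terminal phase left at day 30 (720 h) is 2^(−720/167) = 5.0% or 2^(−720/242) = 12.7%. The upper bound on what remains, as a share of peak, is then:

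- 167 h: 0.2586 × 0.0504 = 1.3%.
- 242 h: 0.2345 × 0.1272 = 3.0%.

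Repeating this with the predicted sixth-dose values in 7.1.4.2 (109,618 ng/mL and 3,577,275 ng·h/mL) gives 1.4% and 3.1%, so repeat dosing hardly changes the bound.

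**4. Expected number of events.** Planned active-arm patients: 24 (Section 5). Section 7.1.6.4 describes highly effective contraception as failing in under 1% per year; take 1%. The number of women of childbearing potential on active drug is not given; assume 12, range 6 to 24. Over days 31 to 90 (60 days): 12 × 0.01 × 60/365.25 = 0.02 pregnancies, range 0.01 to 0.04.

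**The case against.** The best case for leaving 9.8 alone has four parts.

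- **The two periods serve different purposes.** Contraception is a precaution and 9.8 a reporting duty; nothing in the protocol says they must end together. This stands in part. The mismatch is not a contradiction, but the visible text gives no reason for stopping reports 60 days sooner.
- **Little drug is left at day 30.** This stands. A reader might reason from the half-lives alone that 5% to 13% of the post-dose level remains, or that the limit stops 5 to 20 days short of five half-lives (about 35 to 50 days) and should move to about 51 days. The documents do not support that. The 5% to 13% needs single-exponential decline from peak, which the 5 mg/kg values in 7.1.4.2 rule out. The protocol uses five half-lives only for washout of other investigational agents, not for pregnancy reporting.
- **The outcomes that matter are already covered.** Largely true. It would be wrong to read 9.8 as ending follow-up, or the reporting of adverse outcomes, at day 30. Whether the follow-to-completion sentence reaches later pregnancies is open to reading, because it presupposes an initial report. Normal pregnancies starting after day 30 are still not clearly covered.
- **The yield is close to nil.** Also true, at about 0.02 expected pregnancies under the assumptions above. That limits the priority of the change, but the change costs little.

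The consent pages are not in the text reviewed and the Study Reference Manual was not available; either may already ask patients to report later pregnancies.

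**Conclusion.** The point holds as a misalignment of dates within the protocol. Reporting under 9.8 stops 60 days before the pregnancy-avoidance period in 7.1.6.4, and nominally 88 days before the one in the synopsis and 5.1.1. No visible section requires an initial report of an otherwise uncomplicated pregnancy that starts in between.

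This conclusion needs no half-life argument. Residual exposure adds little to it: at most about 1.3% to 3.0% of peak at day 30, based on mean values from single doses in healthy volunteers and on the 5 mg/kg half-life lying within the stated range. A reader might infer that a fetus conceived after day 30 would be exposed at a harmful level. The visible text gives no threshold for fetal effect, so that is neither shown nor excluded.

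No endpoint, analysis or dose-escalation decision is affected. Severity is low: a cheap improvement to the completeness of the safety record.

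**What to change.** - In 9.8, replace the 30-day limit with the end of the required contraception period, at least 90 days after the last dose.
- At the End-of-Study visit, tell patients to notify the site of any pregnancy up to that date.
- Use one contraception end date in the synopsis, 5.1.1, 7.1.6.4 and 9.8, so that the reporting period has a single anchor.

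The cost is protocol and consent wording, one instruction at a visit that already exists, a longer period of passive reporting, and outcome follow-up of any extra pregnancy reported. No visits or tests are added.
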